### **7.6.6. Event-Free Survival Analysis (EFS)**

EFS is defined as time from study randomization to the date of induction treatment failure,

## Statistical Analysis Plan

Study code PrE0905

Version Final V3

Date 09 November 2023

relapse after CRc or to death from any cause after CRc, whichever comes first. For patients alive without induction treatment failure or relapse after CRc, EFS will be censored at the date of the last disease evaluation.

The main analysis of EFS is to set the event date for induction treatment failure on day 1 of randomization.

A sensitivity analysis of EFS will be performed where follow-up will be censored at the start of transplantation (if transplant was done before the date of the last disease evaluation).

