Patients who achieve CR or CRi can proceed to post remission consolidation therapy on study (if otherwise eligible) or may proceed to allogeneic transplant if desired. Patients who do not achieve CR/CRi are removed from study.

Patients who go to transplant or any other non-protocol leukemia directed therapy will complete an end of treatment visit, and will be followed for relapse and survival only.

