#### 5.2.2 Consolidation

Patients deemed suitable by the treating investigator may proceed to allogeneic TRANSPLANT at any time after induction or after 0-4 cycles of chemotherapy consolidation.

Patients will continue to receive the same study drug (gilteritinib or midostaurin) assigned during induction for consolidation.

**NOTE:** Patients are not eligible to proceed to consolidation on study unless bone marrow samples are obtained for Minimal Residual Disease (MRD) at the time of CR/CRi.

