The final analysis of EFS and OS will be performed when the full information of EFS is reached (i.e., 110 events have occurred). Estimates of EFS and OS, including medians and confidence intervals, will be calculated using the Kaplan-Meier method. Comparison of EFS and OS between treatment arms will be conducted using the one-sided stratified log-rank test with FLT3 mutation (TKD vs ITD), FLT3-ITD mutation signal ratio (high  $\geq 0.5$  vs. low  $<0.5$  of FLT3 Wild Type), and NPM1 mutation status, the same stratification factors used in randomization. Cox proportional hazards models, stratified on the same factors above, will also be used to assess the treatment effect.

A sensitivity analysis of EFS will be performed where follow-up will be censored at the start of transplantation.

Comparison of CRc rate, EFS and OS between treatment arms will also be conducted in patients with de novo AML, t-AML and AML-MRC separately; and in patients with favorable, intermediate, and adverse risk separately, determined by 2017 ELN risk classification.

To determine the predictive value of Minimal Residual Disease (MRD) positivity and negativity post induction therapy. EFS and OS of the patients who achieved MRD negative after induction will be compared with those who did not. All CRc patients who have MRD response evaluated post induction will be included into this analysis. The interaction of treatment and MRD status will be tested in the Cox regression model. If a strong interaction effect is detected, the treatment effect will be looked at within MRD+ and MRD- patients separately.

The correlation between MRD by molecular studies and morphology will be assessed. McNemar's test will be used to assess the concordance of the measurements.

For patients who are FLT3 mutation positive after induction and administered consolidation, the FLT3 mutation negative CRc rate after first cycle of consolidation and their corresponding 90% confidence intervals will be given by treatment arm.

To assess the correlation of FLT3 mutation with outcome, the EFS and OS of those patients with FLT3-TKD mutation will be compared with patients with FLT3-ITD mutation. Among those patients with FLT3-ITD mutation, EFS and OS will be compared among those with ITD signal ratio >0.5 with those ≤ 0.5 of FLT3 Wild Type.

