## **2. INTRODUCTION**

### **2.1. Objective of the Statistical Analysis Plan**

This statistical analysis plan (SAP) describes the planned analysis of the safety and efficacy data from this study. A detailed description of the planned tables, figures and listings (TFLs) to be presented in the analysis is provided in the accompanying TFL template document.

The intent of this document is to provide guidance for the analysis of data related to safety and efficacy to describe any applicable statistical procedures. In general, the analyses come directly from the protocol, unless they have been modified by agreement between the Sponsor and Quality Data Services, Inc. (QDS). A limited amount of information concerning this study (e.g., objectives, study design) is summarized to help the reader interpret the accompanying TFL templates. That information is not a synopsis of the study and does not require review or approval because it is simply extracted from the protocol. Attached signatures indicate approval of the statistical analysis sections of the SAP, as well as accompanying TFL templates. These sections must be agreed upon prior to database lock. When the SAP and TFL templates are agreed upon and finalized, they will serve as the template for a portion of this study's report.

This SAP supersedes the statistical considerations identified in the protocol; where considerations are substantially different, they will be so identified. If additional analyses are required to supplement the planned analyses described in this SAP, they may be performed and will be identified in the appropriate section of the study report. Any substantial deviations from this SAP will be agreed upon between the sponsor and QDS. Deviations from this SAP, both substantial and non-substantial, will be documented in the study report. Any updates to their respective analyses, study designs, and TFL presentations after this SAP is finalized and approved will be documented in a running Note to the SAP document.

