## 8. SUMMARY OF CHANGES FROM PROTOCOL-SPECIFIED ANALYSES

No changes are planned.

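### SAP 7.6.6 adds an undeclared condition to the transplant-censored EFS analysis; read literally, a death after transplant with no intervening disease evaluation stays an event

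*SAP*

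**What the plan says.** The two documents describe the same named analysis differently.

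- **Protocol 12.2.2:** "A sensitivity analysis of EFS will be performed where follow-up will be censored at the start of transplantation". No condition is attached.
- **SAP 7.6.6:** follow-up is "censored at the start of transplantation (if transplant was done before the date of the last disease evaluation".

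The rest of SAP 7.6.6 decides what happens when that condition is not met. After remission, the EFS event is "relapse after CRc or to death from any cause after CRc, whichever comes first". The ordinary censoring rule is restricted to living patients: "For patients alive without induction treatment failure or relapse after CRc, EFS will be censored at the date of the last disease evaluation".

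On differences between the documents, SAP 2.1 says "This SAP supersedes the statistical considerations identified in the protocol; where considerations are substantially different, they will be so identified". SAP section 8, where changes would be listed, says "No changes are planned".

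On timing, Protocol 5.2.2 says suitable patients "may proceed to allogeneic TRANSPLANT at any time after induction or after 0-4 cycles of chemotherapy consolidation". Under Protocol 5.2.1 they have an end of treatment visit and then "will be followed for relapse and survival only". Protocol 7.2 sets visits every 3 months for the first 2 years, with a window of 1 month either way. Neither document defines a disease evaluation for the purpose of the SAP condition.

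**The concern.** A censoring rule should depend only on what is known up to the censoring time. The SAP condition looks forward: whether a patient is censored at transplant depends on whether disease was evaluated later. For a patient who dies, that depends partly on how long the patient survived and on when the next assessment fell.

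The purpose of the analysis is to show EFS without the outcomes of transplant. If some deaths after transplant remain as events, the result answers a mixed question. Transplant is the investigator's choice in an open-label trial, so uptake could differ by arm; any retained deaths would then weigh more on the arm with more transplants. With the term undefined, two programmers could also classify the same death differently.

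**Working it through.** **1. The plan's own EFS figure.** Inputs from Protocol 12.2.2: 38% hazard reduction (HR 0.62), one-sided 0.05, 80% power, about 110 events.

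- Schoenfeld: 4 × (1.645 + 0.842)² / (ln 0.62)² = 24.73 / 0.2285 = 108.2, so 109.
- Freedman: (1.62 / 0.38)² × (1.645 + 0.842)² = 18.17 × 6.18 = 112.4, so 113.

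The stated 110 reproduces, and it belongs to the main analysis, which this point does not touch.

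**2. Both rules applied to four histories** (months from randomization; all transplanted in first remission at month 4):

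| History | Protocol 12.2.2 | SAP 7.6.6, literal |
|---|---|---|
| Last evaluation 3.5, death 5 | censored at 4 | **event at 5** |
| Evaluation 7, death 8 | censored at 4 | censored at 4 |
| Relapse found at 10 | censored at 4 | censored at 4 |
| Last evaluation 3.5, alive | censored at 4 | censored at 3.5 |

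In the first row the transplant does not precede the last evaluation, so transplant censoring is not triggered. The last-evaluation rule does not apply because the patient is not alive. The event definition is all that remains, and it counts the death. The fourth row changes a date but no event status. Only the first row changes what is counted.

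**3. How many deaths.** The documents give neither transplant uptake nor the share of transplanted patients who die before a further evaluation. Assume 30–70% uptake and a 2–10% share. Deaths kept as events = 170 × uptake × share:

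- low: 170 × 0.30 × 0.02 = 1.0
- middle: 170 × 0.50 × 0.05 = 4.2
- high: 170 × 0.70 × 0.10 = 11.9

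**4. Effect on the HR.** A simulation with no true treatment effect used 100,000 patients per arm. Its assumptions, none from the documents, were 25% induction failure in each arm, 12-month median time to relapse, transplant at months 2–6, and the deaths in question within 3 months of transplant. Transplant was possible only in patients still in remission, so fewer deaths are retained than in step 3.

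| Uptake (gilteritinib vs midostaurin) | Share dying unevaluated | HR, protocol rule | HR, literal SAP rule | Ratio | Extra events per 170 |
|---|---|---|---|---|---|
| 50% vs 50% | 2% | 1.003 | 1.003 | 1.000 | 1.0 |
| 50% vs 50% | 5% | 0.999 | 0.998 | 0.999 | 2.6 |
| 50% vs 50% | 10% | 1.006 | 1.004 | 0.998 | 5.2 |
| 60% vs 40% | 2% | 0.993 | 0.999 | 1.006 | 1.0 |
| 60% vs 40% | 5% | 0.993 | 1.007 | 1.014 | 2.5 |
| 60% vs 40% | 10% | 0.996 | 1.022 | 1.026 | 5.1 |
| 70% vs 40% | 2% | 1.000 | 1.010 | 1.010 | 1.2 |
| 70% vs 40% | 5% | 1.009 | 1.033 | 1.024 | 2.8 |
| 70% vs 40% | 10% | 0.994 | 1.044 | 1.050 | 5.6 |

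The ratio compares the two rules on the same simulated patients. It stays at 1.00 with equal uptake and rises to 1.05 in the most unequal case tried. The shift is against the arm with more transplants.

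**The case against.** The best defence is that the parenthesis reuses the phrase that, earlier in SAP 7.6.6, gives the censoring date for living patients without an event. Its natural job is then to order two censoring dates: use the transplant date if it comes before the date on which the patient would otherwise be censored. On that reading, deaths after transplant are still censored at transplant, and the wording is a harmless operational detail that SAP 2.1 would not require to be flagged as substantially different. This is probably what was meant, and it largely stands as an account of intent. It does not settle the text, which attaches the condition to the whole analysis and is silent on patients who die.

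Three stronger inferences are tempting, and the documents do not support them.

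- *That the SAP selectively removes later deaths and relapses.* Removing them is the protocol's own rule. The documents differ in event status only for deaths with no evaluation after transplant.
- *That such a death is the typical early transplant death, because no marrow is scheduled after transplant.* A disease evaluation is not defined as a marrow, and Protocol 9.8 allows relapse to be declared from blood or extramedullary disease. With the Protocol 7.2 visits, the exposed period is plausibly the first 3–4 months, but no frequency is given.
- *That the arm with more transplants is heavily penalised.* The simulated shift is small even with a 30-point difference in uptake.

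**Conclusion.** The point holds as a wording fault of minor weight. SAP 7.6.6 adds a condition absent from the protocol and not declared in section 8. Applied literally, it makes censoring depend on information from after transplant for one group of patients. It would be wrong to say that the SAP intends to count early transplant deaths; it fails to exclude that result.

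The size rests on assumed rates: about 1–12 deaths among 170 patients, and an HR shift of at most about 5% in the scenarios tried, disappearing when uptake is equal. Only one sensitivity analysis of a secondary endpoint is affected. The primary endpoint, the main EFS analysis, overall survival and the 110-event target are unaffected.

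**What to change.** Delete the parenthesis in SAP 7.6.6 and state: *Patients transplanted before any EFS event are censored at the date of transplantation, whatever is observed afterwards; relapses and deaths after transplant are not counted.* This matches Protocol 12.2.2.

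If the sponsor prefers the last evaluation date when it falls before transplant, limit that to patients who are alive and event-free and list it in SAP section 8 as a change. It is not the protocol rule: in the fourth history above it censors at month 3.5 and not at month 4.

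The cost is one sentence, which can go in the running Note to the SAP that section 2.1 provides for, and one line of code. No new data are needed: transplant ends protocol treatment, and Protocol 7.2 already has anticancer therapy given in the current remission documented. The analysis would have slightly fewer events than under the literal wording.

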### 7.6.7. Overall Survival (OS)

OS is defined as the time between randomization and death from any cause. The censored follow-up time for patients without death information is the date of last contact.

The final analysis of EFS and OS will be performed when the full information of EFS is reached (i.e., 110 events have occurred). Estimates of EFS and OS, including medians and confidence intervals, will be calculated using the Kaplan-Meier method. Comparison of EFS and OS between treatment arms will be conducted using the one-sided stratified log-rank test with FLT3 mutation (TKD vs ITD), FLT3-ITD mutation signal ratio (high  $\geq 0.5$  vs. low  $<0.5$  of FLT3 Wild Type), and NPM1 mutation status, the same stratification factors used in randomization. A multivariate Cox proportional hazards model, stratified on the same factors above, will also be used to assess the treatment effect.

Comparison of EFS and OS between treatment arms will also be conducted in patients with de novo AML, t-AML and AML-MRC separately; and in patients with favorable, intermediate, and adverse risk separately, determined by 2017 ELN risk classification.

## Statistical Analysis Plan

Study code PrE0905

Version Final V3

Date 09 November 2023

### 7.7. Interim Analysis

There is an Interim Analysis of FLT3 Mutation Negative CRc Rate and EFS in this study.

An interim futility analysis of FLT3 mutation negative CRc rate will be performed when 90 (i.e., 50% of 179) patients have MRD response data available. The PrECOG Data Safety Monitoring Board (DSMB) may consider stopping the study for inefficacy if the observed FLT3 mutation negative CRc rate in the gilteritinib arm is lower than the control arm. The FLT3 mutation negative CRc rate (and CR rate) with two treatment arms combined will also be calculated. Upon the approval of the DSMB, it may be released to the study team to guide the design in other AML Phase III trials.

When the last patient has completed the induction treatment and all patients have MRD response data available, the final analysis of FLT3 mutation negative CRc rate will be performed. At that time, if the information fraction of EFS >50% (i.e., more than 55 EFS events have occurred), an interim futility analysis of EFS will be performed as well. Otherwise, the interim analysis of EFS will be performed later until 50% of information is reached. In the interim analysis of EFS time, the Kaplan-Meier curve for each arm and the point estimate and two-sided 90% confidence interval of hazard ratio (gilteritinib arm vs. control arm) will be provided. If the lower bound of the 90% confidence interval of HR is above 1, the study may be permanently terminated for inefficacy in EFS.

## 8. SUMMARY OF CHANGES FROM PROTOCOL-SPECIFIED ANALYSES

No changes are planned.

## **9. REFERENCES**

References are provided in the protocol.

## **10. TABLES, FIGURES, AND LISTINGS**

See separate template document.

# Statistical Analysis Plan

Study code PrE0905

Version Final V3

Date 09 November 2023

## 11. APPENDIX

### 11.1. Appendix I. Study Procedure and Parameters

Procedures	Pre-screen	Screening/ Prior to Randomization	Induction*					Consolidation*			End of Treatment 	Follow - Up 
			Daily	Weekly	Day 21 from Start of Cycle 1 Induction	Prior to 2 nd Induction, if Applicable	End of Induction	Prior to Each Consolidation Cycle	Weekly	End of Consolidation		
Written Informed Consent	X 	X										
Disease Characteristics 		X										
Medical/Surgical History		X										
Assessment of Baseline Signs and Symptoms		X										
Height		X										
Physical Exam		X	X 			X		X	X		X	
Vital Signs (Temperature, Pulse, Blood Pressure)		X	X 			X		X			X	
Weight 		X				X		X			X	
BSA		X				X		X			X	
Performance Status		X		X		X		X			X	
CBC/Differential/ Platelet 		X	X 			X		X	X 		X	
Chemistry 		X		X 		X		X	X 		X	
Liver Functions 		X		X 		X		X	X 		X	
Thyroid Function Test (T4 & TSH) 		X									X	
Serum Pregnancy Test 		X										
Left Ventricular Ejection Fractions (MUGA or ECHO) 		X				X 						
12-Lead ECG (QTcF Interval)		X 		X 	X 	X 		X 				
Local Bone Marrow Aspirate Biopsy (Mandatory)	X 				X 		X 			X		
Research Bone Marrow Samples Submission (Mandatory) 	X 						X			X		

## Statistical Analysis Plan

Study code PrE0905

Version Final V3

Date 09 November 2023

Protocol Therapy Administration 			X					X			
Concomitant Medications		X	X 			X		X			
Adverse Events Assessment			X 			X		X		X	
Survival Status										X	

- \* Scheduled Visits: Delay due to holidays, weekends, bad weather or other unforeseen circumstances will be permitted.
- 1 Any patient undergoing bone marrow biopsy with suspicion of or known diagnosis of AML will be asked to sign a Prescreening Consent in order to obtain baseline immunophenotyping and determination/confirmation of FLT3 status and obtain research samples for the study prior to randomization. FLT3 (includes signal ratio), NPM1 and DNMT3 mutation status will be performed on all patients. These tests will be completed at Central Labs. See Section 13.1, Invivoscribe Lab Manual and PrE0905 Lab Manual for details. FLT3 and NPM1 mutation status results must be available on all patients. Patients must have known FLT3 mutation and will be stratified according to TKD vs. ITD FLT3 mutation. Patients with FLT3-ITD mutation will undergo further stratification with NPM1 mutation status (positive vs. negative) and signal ratio (high  $\geq 0.5$ ] vs. low [ $<0.5$ ] of FLT3 Wild Type).  
For patients who are registered with tissue submitted for the study and are FLT3 negative or other condition, no further information will be collected after baseline demographics, sample submission, sample results and final diagnosis.
  2. Record date of diagnosis (date of diagnostic bone marrow biopsy), primary tumor type, histology, cytogenetics and molecular markers.
  - 3 **Induction:** Daily if admitted to hospital, otherwise weekly until count recovery.  
**Consolidation:** May be done locally after Day 8 visit per institutional guidelines.
  4. Per Study Parameters and as clinically indicated.
  - 5 CBC with differential and platelet count which includes WBC, ANC, Platelets, Hemoglobin, and Hematocrit. Additionally, required within 24 hours prior to each cycle of chemotherapy.
  - 6 **Induction:** Differential daily until disappearance of peripheral blasts and then again when WBC over 500. Differential twice weekly at nadir, after peripheral blasts gone and while WBC  $<500$ .  
**Consolidation:** Twice weekly.
  - 7 BUN/creatinine, uric acid, sodium, potassium, chloride, glucose, calcium, magnesium, and phosphorus. Additionally, required within 24 hours prior to each cycle of chemotherapy.
  - 8 **Induction:** Twice weekly.  
**Consolidation:** Weekly.
  - 9 AST, ALT, and total bilirubin. If total bilirubin  $\geq 2$ , obtain direct bilirubin (if direct bilirubin  $\geq 2$ , refer to Section 6.1 for Dose Modifications/Interruptions). Additionally, required within 24 hours prior to each cycle of chemotherapy.
  - 10 Thyroid Function test results not required for randomization.
  - 11 Required for sexually active females of child-bearing potential.
  - 12 LVEF must be obtained before initiating second induction cycle (if applicable) and must use same method as initial assessment.
  - 13 Perform 12-lead ECG in triplicate (3 separate ECGs recorded at least 5 minutes apart) following a 10-minute resting period. Patient may not have QTcF interval  $>500$  msec or Long QT Syndrome.

## Statistical Analysis Plan

Study code PrE0905

Version Final V3

Date 09 November 2023

### Calculation of QTc interval using the Fridericia formula:

[https://qxmd.com/calculate/calculator\\_48/ecg-corrected-qt37,38,39](https://qxmd.com/calculate/calculator_48/ecg-corrected-qt37,38,39)

- 14 Perform 12-lead ECG in triplicate (3 separate ECGs recorded at least 5 minutes apart) following a 10-minute resting period prior to gilteritinib or midostaurin administration (ECG within 1 hour of dosing preferred). The mean QTcF of the triplicate ECG tracings will be used for final treatment decisions and AE reporting. If the mean of the triplicate QTcF is >500 msec, then triplicate ECGs will be repeated (within 2 hours). If the repeat ECGs confirm a mean QTcF >500 msec, refer to Section 6.1.2 and Section 6.1.3 for further guidance on treatment decision. In addition, on Cycle 1, Day 15 if QTcF is increased >30 msec over screening, repeat ECG on Day 16 and refer to Section 6.1.2 for further guidance on treatment decision.

### Induction (First Induction)

Day 8, Day 15 and Day 21

### Second Induction and Consolidation

Day 1 of each cycle

**See footnote 13 for Calculation of QTc interval using the Fridericia formula.**

- 15 Perform 12-lead ECG in triplicate (3 separate ECGs recorded at least 5 minutes apart) following a 10-minute resting period.  
**See footnote 13 for Calculation of QTc interval using the Fridericia formula.**
- 16 +/- 1 day window (Delays due to holidays, weekends, or other unforeseen circumstances will be permitted).
- 17 For patients that receive 1 cycle of induction, no later than Day 60 after initiation of first cycle of induction therapy. For patients that receive 2 cycles of induction, no later than Day 60 after initiation of the second cycle of induction therapy (i.e., Day 84-105). [MRD sample will be obtained by Day 60 on all patients even if counts have not recovered. The only exception is a patient who has been declared a relapse based on blood counts.]
- 18 Optional, at time of relapse, bone marrow samples are requested to be sent for correlative studies (Section 13.1).
- 19 Mandatory Research Bone Marrow Samples: See Section 13.1, Invivoscribe Lab Manual and PrE0905 Lab Manual for details.

